According to recently published data, 25% of the U.S. population is comprised of adults with disabilities, with approximately 6% of the sample having a hearing disability. Prevalence of hearing disabilities increases with age and poverty level.ⁱ These estimates are likely conservative due to (a) their limitation to non-institutionalized adults, (b) sampling method, and (c) their reliance on self-identification. People who are culturally Deaf view their deafness as a difference, and thus do not self-identify as having a disability. People who are culturally Deaf view themselves as a linguistic minority, bonded by their use of a common signed language, shared experiences, and shared values and norms (e.g., collectivism, rejection of the disability label, Deaf pride, solidarity, directness, expressiveness).ⁱⁱ Like other minority populations in the United States, people who are culturally Deaf are at risk for developing diabetes and acute complications related to unmanaged diabetes. Also, there is a diabetes subtype, maternally inherited diabetes and deafness (MIDD) that, although rare, accounts for a portion of diabetes cases in the deaf population.^{iii,iv} Increased risk is associated with low rates of health literacy due to lack of accessible health information^v and isolation from the hearing world.^{vi, vii} Further, because the language and communication barrier for the population is so pervasive, it is anticipated that standard transition of care materials may overestimate the diabetes knowledge of people who are Deaf and transitioning into independent care routines. As such, materials may need to be restructured to account for any knowledge deficits. This project will not only evaluate an educational intervention, but the research is designed in such a way as to measure if there are any between-group differences in knowledge about diabetes based on whether the subject has a diabetes diagnosis or not.

Given the language barrier and insufficient provision of certified sign language interpreters during medical visits, we hypothesize that people who are Deaf without a diabetes diagnosis and those who are Deaf with a diabetes diagnosis will have similar levels of diabetes knowledge.

The aim of this study is to evaluate an ASL-interpreted diabetes educational intervention to quantitatively demonstrate a need for diabetes educational outreach materials to be accessible to people who are Deaf and rely on ASL for clear and effective communications.

SURVEY OF THE FIELD

This project addresses disparate health outcomes related to health literacy levels of people who are Deaf. The Agency for Healthcare Research and Quality (AHRQ) within the U.S. Department of Health and Human Services, notes that low health literacy among all adults in the United States results in adverse healthcare outcomes.^{viii} Individuals who are Deaf and hard of hearing have been shown to have lower health literacy levels compared to their hearing counterparts with

the same level of formal education.^{ix} Dammeyer and Chapman (2017) also found corroborating evidence that people with hearing loss have an increased risk of developing a physical illness compared to the general population.^x Consequently, the low levels of general health literacy among people who are Deaf increases risk for developing chronic illnesses^{xi, xii, xiii} including diabetes.^{xiv} One comparative study found that subjects who were Deaf compared to those who were not had similar rates of diabetes diagnoses when blood sugar levels were tested. However, the subjects that were Deaf had lower levels of awareness about their blood sugar levels, often not self-reporting that they had diabetes when explicitly asked, resulting in poor self-management of their condition.^{xv}

Quantifying the prevalence of diabetes among the target population is difficult due to the language barrier and broad health data surveys not consistently accommodating ASL. However, there is evidence that people who are Deaf have a high prevalence of health-related risk factors associated with diabetes. Dair, Ellis, and Lieberman (2006) using body mass index (BMI) national averages for the age group as the comparison found that 23.2% of their sample of children (6-11 years old) who were Deaf were overweight, and 27.2% were at risk for becoming overweight.^{xvi} According to the authors, these findings are significant given that being overweight as a child is correlated to adulthood obesity, which in turn is associated with diabetes and other illnesses (e.g., hypertension). Also, there is a diabetes subtype, maternally inherited diabetes and deafness (MIDD) that, although rare, accounts for a portion of diabetes cases in the deaf population.^{xvii, xviii}

Barnett et al. (2016; 2017) developed a standardized, computer-based, linguistically adapted public health survey. They asserted that health data from the culturally Deaf are not included in public health surveillance due to the survey instruments not being available in ASL. As such, the specific public health needs of this population are unknown.^{xix} This lack of data was posited as a contributing factor to disparate health outcomes because the results of health surveillance studies are used to develop population-specific health outreach, resources, and services. The results of the adapted tool indicated that the sample of Deaf respondents reported higher rates of emergency department use than the general population (16% compared to 6.9% visiting an emergency room twice in one year), as well as a higher propensity to forego utilizing health services due to the costs (22.7% compared to 8.1%).^{xx} Extrapolations from these data support the notion that people who are Deaf may present with more acute symptoms and suffer greater health consequences as a result of the confluent factors of delays in treatment and limited health literacy. The research not only provided evidence of disparate health issues experienced by people who are culturally Deaf, but its findings suggest that health disparity outcomes are associated with language barriers, showing a critical need for ASL-adapted health education programs.

As an example of the adverse health impacts of language and communication barriers in the medical context, one could look to research on medication adherence. Many people, for various reasons, struggle with managing their medications and lack of adherence to medication regimens is associated with poorer health outcomes, including 40% of nursing home admissions in people

with type 2 diabetes.^{xxi} That statistic may be exponentially higher in the population of people who are Deaf. Ferguson and Liu (2015) conducted focus groups with 20 subjects who were Deaf or hard of hearing and found that these subjects struggled with the complexity of the written materials that were given to them as a means of communicating information about their medicines.^{xxii} In this study, five of the participants (25%) reported adverse events stemming from a lack of understanding of medication instructions or warnings. These included excessive drowsiness from taking too much medication, dizziness caused by taking two interacting medications together, and needing to pull-over while operating a vehicle under the influence of a prescribed narcotic.^{xxiii} In another study, 40% of focus group participants who were Deaf were unaware that an adverse reaction could result from not taking their medications appropriately.^{xxiv} Two-thirds (67%) of these respondents stated that they would better understand the information if provided in ASL.^{xxv} In sum, while one of the greatest barriers faced by people who are culturally Deaf are communication-based,^{xxvi} little has been done to ensure that health education and outreach materials are effectively communicated to the target population.

PROJECT DESIGN

Population: Individuals who are Deaf and who rely on ASL for clear and effective communication/comprehension are the primary target population for this research. Estimates of the size of this population range from 500,000 to 2 million,^{xxvii, xxviii} but these estimates are hampered by problems with systemic data collection. Unfortunately, the United States does not document the number of individuals that use ASL as their primary language either through the Decennial Census, the American Community Survey (ACS) or through any government agency. These surveys are administered in written English text, which is not well understood by people who are Deaf and rely on ASL, for whom reading comprehension level has been estimated to be at the fourth-grade level.^{xxix, xxx, xxxi} Even if written English is understood by the respondent, the ACS and Decennial Census do not include ASL as an option in their questions regarding household language.^{xxxii} Finally, the surveys reflect a hearing primacy evident in the emphasis on spoken language, making it difficult to answer What languages other than English are spoken in the household? if one's native language is ASL.

Screening and inclusion process: Study subjects (n=41) were recruited by project partners, Deaf Link, using ASL-interpreted video recruitment and staffers who are Deaf to communicate with prospective subjects via videophone. Twenty-one subjects were Deaf with a self-reported diabetes diagnosis and 20 subjects were Deaf without a diabetes diagnosis (self-reported).

Inclusion criteria was the provision of informed consent, aged 18 years and older, Deaf whose primary language is ASL with or without a diabetes diagnosis.

Exclusion criteria was minors, people whose primary language is *not* ASL, individuals unable to provide consent due to impaired decision-making.

Intervention: The project produced a video-based ASL interpreted diabetes educational intervention (ASL-ADE). The content for the ASL-ADE intervention was derived from diabetes

health information regarding symptoms and risk factors that are published by the American Diabetes Association and subject matter experts [name], Professor of Medicine, Emory University School of Medicine, Division of Endocrinology, Metabolism and Chief of Diabetes and Endocrinology, Grady Health Systems; and [name], MS, RD, CDE, CDN, Assistant Program Director - Emory Latino Diabetes Education Program at Emory University School of Medicine. In collaboration with our subawardee, Deaf Link, Inc., the ASL-ADE scripts were reviewed for content to ensure clarity and determination of ASL signs to be used to convey the meanings. This approach allowed for the collaborative inclusion of Deaf community stakeholder's knowledge, perspectives, and experience related to ASL interpretation of health concepts. Certified ASL interpreters and representatives from the Deaf population met to determine the optimal ASL terms for the content. Based on their expertise, scripts were refined and revised as necessary. The ASL-ADE video intervention was produced through a multi-step process that consisted of pre-production planning, video production, quality control, and post-production. The final intervention was a four-part video series:

1. What is Type 2 Diabetes?
<https://youtu.be/Nmy84TqxMA8>
2. How to Check Your Blood Glucose
<https://youtu.be/QYJy whole>
3. Understanding Hypoglycemia and Hyperglycemia
<https://youtu.be/wOOWr7Bzd4o>
4. Exercise and Nutrition Can Help Manage Diabetes
<https://youtu.be/wWB-xOabb9U>

Outcome: All visits were conducted individually through a virtual meeting platform and included a certified ASL interpreter who is bound by professional ethics codes regarding confidentiality. Recruitment and intervention were ongoing from October to December 2020 (rolling enrollment, ~30day follow-up). Though the questionnaires are self-report, they were administered by the PI's and the participants' answers directly input into the online Qualtrics survey.

Data was collected using study-specific ASL-interpreted questionnaires designed by project personnel. The questionnaire items that measure diabetes knowledge included in the ASL-ADE intervention were forced choice, closed-ended questions to allow for a total score ranging from 0 correct to all correct. Covariates included self-reported information of interests to the study such as gender, age, educational level, level of pre-study exposure to diabetes-related health information, and health behaviors (e.g., diet, exercise, healthcare maintenance). The content of the post-test (immediate) and post-test 30-day follow-up were identical. The pretest contained demographics questions that we only asked once.

Using a pretest-posttest (immediate), 30-day posttest quasi-experimental design, we tested the effect of the educational intervention on knowledge about diabetes and related health behavior changes. The dichotomous X variable was diagnosis status, and the outcome variable (Y) was test scores. Any observed group mean differences, or lack thereof, were anticipated to be predicted by membership in the group. The pre and posttest intervention questionnaires adapted, in part,

from the CDC's *Behavioral Risk Factor Surveillance System (BRFSS)* were administered as follows:

Phase One:

Step 1 - Pretests

- Section 1: Your Awareness of Diabetes
- Section 2: Your Health Behaviors
- Section 3: Diabetes Health Literacy
- Section 4: Demographics

Step 2 - Research Participants in the intervention Group Views Videos

Step 3 - Posttest Immediate

- Section 1: Diabetes Health Literacy

Phase Two:

Posttest ~30 Days Later

- Section 1: Diabetes Health Literacy
- Section 2: Your Health Behaviors

Debriefing where correct answers are provided for the Diabetes Health Literacy questionnaire and the intervention offered to the control group.

Data handling: The questionnaire based raw data will be electronically stored in the Qualtrics survey platform, using code linkage. A master data file, downloaded from Qualtrics, will be kept as a password protected Excel file to ensure access to unadulterated raw data. Georgia Tech's IT systems continuously monitor for adverse events.

Archiving of data. Data is archived for at least 10 years.

Official Title: American Sign Language-Accessible Diabetes Education

NCT Number: NCT03980808

Statistical Analysis Plan: December 16, 2021

STATISTICAL ANALYSIS PLAN

AMERICAN SIGN LANGUAGE – ACCESSIBLE DIABETES EDUCATION

1. Aims and Objectives

This pilot study sought to demonstrate the impact of an educational information that provides diabetes management information to people who are Deaf in American Sign Language (ASL). Project activities produced two videos in ASL created from standard diabetes educational interventions. Using a pretest-posttest quasi-experimental design, we evaluated the effect of the educational intervention ASL videos on knowledge about diabetes and related behavioral health. These changes were measured through study specific instruments that were based on the content of the educational interventions. Behavioral changes were self-reported. These study instruments were administered to the participants through interviews facilitated by Advanced Certified ASL interpreters.

2. Sample Size

A pilot study with 40 participants who are Deaf and use ASL as their primary means of communication.

3. Outcomes

This section will present the outcomes investigated to answer the study aims and objectives. The analyses are described in Section 5 Analyses.

Primary Outcomes

Change in knowledge as measured by composite score of the study specific instrument based on the educational intervention.

Changes in self-reported behaviors related to diet, exercise, and smoking habits as measured by a composite score of a study specific instrument based on the information presented in the educational intervention ASL videos.

4. Populations and SubGroups to be Analyzed

Subjects included those who are Deaf and use ASL as their primary means of communication. Subjects with and without diabetes were included in the protocol. All included study subjects completing the whole study period (i.e. pre and 30 day post) will be seen as the primary population for the analysis. Subjects who did not complete the 30 day post-test are excluded from the analysis.

5. Analysis

All outcomes will be presented using descriptive statistics; normally distributed data by mean and standard deviation and skewed distributions by median and interquartile range (IQR). Binary and categorical variables will be presented using counts and percentages. SPSS statistical software version 26 (SPSS Inc., Chicago IL, USA) will be used for all statistical analysis.

Primary Outcomes

Analysis of change of knowledge will compare differences between the intervention group and the control group as measured by the changes to the composite scores of the knowledge-based test. On factor Analysis of Variance (ANOVA) will be used to compare the differences with an a priori alpha level of 0.05.

Analysis of change in behavior will compare differences between the intervention group and the control group as measured by the changes in the composite scores of the behavioral intervention. On factor Analysis of Variance (ANOVA) will be used to compare the differences with an a priori level of 0.05.

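### The SAP's one-factor ANOVA has no diagnosis term, so a video effect confined to one diagnosis group is diluted and cannot be attributed to that group

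*SAP*

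**What the plan says.** SAP section 5 (Analysis, Primary Outcomes) sets the same test for both primary outcomes.

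- Knowledge: "Analysis of change of knowledge will compare differences between the intervention group and the control group", and then "On factor Analysis of Variance (ANOVA) will be used to compare the differences with an a priori alpha level of 0.05".
- Behaviour: "Analysis of change in behavior will compare differences between the intervention group and the control group", and then "On factor Analysis of Variance (ANOVA) will be used to compare the differences with an a priori level of 0.05".

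I read the opening words of the two ANOVA sentences as a slip for one-factor. Neither sentence includes diagnosis as a factor, an interaction, a stratification or a summary by diagnosis.

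SAP section 4 is headed "Populations and SubGroups to be Analyzed". Its text says "Subjects with and without diabetes were included in the protocol" and then defines a single population of 30-day completers. It names no other subgroup and attaches no analysis to these two.

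The protocol (Project Design, Screening and inclusion process) reports 21 participants with and 20 without a self-reported diabetes diagnosis. Under Outcome it states: "The dichotomous X variable was diagnosis status, and the outcome variable (Y) was test scores". The same section describes an intervention group that views the videos and a control group offered them at debriefing. It gives neither the arm sizes nor the method of allocation.

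**The concern.** Diagnosis is the one factor the protocol's recruitment and its stated explanatory variable are built around, yet the SAP's confirmatory model ignores it. Three consequences follow, each depending on how viewing was distributed over diagnosis.

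1. If both arms contain both diagnosis groups, the one-factor test averages over them. A null result could hide a real effect in one group. A positive result could be read as applying to both when one gained nothing.
2. If the diagnosis mix differs between arms, part of the apparent viewing effect may be a difference between people with and without diabetes. The design is quasi-experimental with no stated allocation method, so balance cannot be taken for granted.
3. If viewing and diagnosis coincide or nearly so, the two effects cannot be separated. The reader needs to be told this.

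Behind all three lies a plain inconsistency: the protocol's explanatory variable is diagnosis, while the SAP's factor is viewing group.

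**Working it through.** **Inputs from the documents.** Alpha 0.05 for each primary outcome (SAP section 5). Planned N 40 (SAP section 2). Recruited 21 + 20 = 41 (protocol). The documents give no power statement, effect size, SD, allocation ratio or dropout rate, so there is no planned figure to reproduce.

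**Assumptions.** 40 completers, 20 per arm, 10 per viewing-by-diagnosis cell, within-cell SD 1, two-sided 0.05, effect d in one diagnosis group and 0 in the other.

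**What the one-factor contrast estimates.** Let p1 and p0 be the share of the responding group in the viewing and control arms. Let δ be the difference in mean change between the diagnosis groups when no videos are seen. Then

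expected contrast = p1·d + (p1 − p0)·δ.

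The first term is dilution and the second is confounding. With equal mix the second term vanishes. If both arms mirror the recruited mix, p1 is 21/41 = 0.51 or 20/41 = 0.49, so the effect is about halved. With 10 per cell it is exactly d/2. No document gives p1 or p0, so halving is conditional.

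**Power at d = 1.0.**

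- One factor, same effect in both groups: 1.0/√(2/20) = 3.16 on 38 df, power 87%.
- One factor, effect in one group only: the contrast is 0.5 and the pooled SD is √(1 + 1.0²/8) = 1.06. The noncentrality is 0.5/(1.06 × 0.316) = 1.49 on 38 df, power 31%. Simulation with fixed cells gives 29%.
- Two-factor main effect of viewing: 0.5/√(2/20) = 1.58 on 36 df, power 34%.
- Interaction: SE √(4/10) = 0.63; 1.0/0.63 = 1.58, power 34%.
- Viewing effect within the responding group: SE √(2/10) = 0.447; 1.0/0.447 = 2.24, power 59% unadjusted and 47% with Bonferroni for two groups.

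**Over a range of d** (effect in one group only, except the second column):

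| d | One factor, same effect in both | One factor | Two-factor main effect (interaction identical) | Within responding group | Same, Bonferroni |
|---|---|---|---|---|---|
| 0.8 | 69% | 22% | 23% | 41% | 30% |
| 1.0 | 87% | 31% | 34% | 59% | 47% |
| 1.5 | >99% | 53% | 64% | 90% | 84% |

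With 30:10 allocation and SD 1 (normal approximation), power for the averaged contrast is about 28% at d = 1.0 and 54% at d = 1.5.

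**Precision of the by-diagnosis estimates.** The 95% half-width is t(0.975, 36) × SE, with t = 2.03.

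- Within one diagnosis group: 2.03 × 0.447 = 0.91 SD.
- Interaction: 2.03 × 0.632 = 1.28 SD.

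Interaction power of 80% would need about 128 participants at d = 1.0, or 56 at d = 1.5.

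**The case against.** The strongest reply is that the two-by-two layout is assumed. No section says that viewing was split within diagnosis, and the only explanatory variable the protocol names is diagnosis. If arm and diagnosis largely coincide, nothing is being pooled and the two-factor model cannot be fitted, or only barely. This stands as a condition on the point. It is why the cell counts must be reported first, and why a fallback statement is needed.

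Second, the subgroup commitment is thin. The word appears only in the heading of SAP section 4, and the text defines one population. In a pilot of 40, not planning subgroup tests is defensible. That is a fair reason to keep by-diagnosis results exploratory. It is not a reason to omit the protocol's own explanatory variable from the model.

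Third, adding diagnosis does little for the main test, which remains an averaged contrast (34% against 29–31%). This also stands. Setting 59% beside 31% would mislead, because 59% is an unadjusted test in a group chosen because it is assumed to respond.

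Fourth, two arguments for expecting different effects should not be pressed. A reader might infer that the protocol's remark about restructuring materials calls for the effect by diagnosis. That remark concerns levels of knowledge, and the protocol hypothesises similar levels in the two groups. That hypothesis also weakens a ceiling argument, which needs one group to start higher. Neither document states an aim of estimating the video effect by diagnosis.

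Last, the SAP is dated December 16, 2021, and the protocol places recruitment and intervention in October to December 2020. Any change of model now is made after data collection and must be presented as such.

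**Conclusion.** The point holds in a limited form. The SAP's model for both primary outcomes omits the factor by which the protocol recruited and which it names as its explanatory variable. Where viewing varied within diagnosis, an effect in one group only is diluted, to about half under equal mix, and cannot be attributed. Where the mix differs between arms, the viewing comparison is open to confounding by diagnosis.

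A reader might infer that such an effect could not be detected at all. The figures do not support this: one-factor power is about 29–31% at d = 1.0 and 53% at d = 1.5, which is low but not nil. A reader might also infer that the two-factor model would rescue a missed effect. It raises power only to about 34% at d = 1.0. Its value is estimation, attribution and adjustment for unequal mix.

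All power figures rest on assumed cell sizes, SD and effects, because the documents give none.

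**What to change.** 1. Reconcile the protocol's explanatory variable (diagnosis) with the SAP's factor (viewing group), and state which comparison each primary test addresses.
2. Report the number of completers in each viewing-by-diagnosis cell.
3. Where both factors vary, fit viewing group, diagnosis and their interaction to both change scores. Keep the viewing effect averaged over diagnosis as the 0.05 test, and say how the two groups are weighted if cells are unequal. Report the viewing effect by diagnosis, and the interaction, with 95% CIs labelled exploratory.
4. If viewing was not split within diagnosis, state that the effect by diagnosis cannot be estimated.
5. Date the change and say that it follows data collection.

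No new data are needed, since diagnosis was recorded at recruitment. With 40 completers, residual degrees of freedom fall from 38 to 36. The main downside is wide by-diagnosis intervals, about ±0.91 SD under the assumptions above, which will support description but not a firm subgroup claim.

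### Does the protocol's list of health behaviors as covariates conflict with the SAP's use of behavior change as a second primary outcome?

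*SAP*

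**What the plan says.** **Protocol, Project Design, Outcome.** The covariate list begins "Covariates included self-reported information of interests to the study such as gender, age, educational level" and goes on to "level of pre-study exposure to diabetes-related health information, and health behaviors (e.g., diet, exercise, healthcare maintenance". Knowledge items are closed-ended "to allow for a total score ranging from 0 correct to all correct"; no scoring rule is given for behavior items. The next paragraph says "we tested the effect of the educational intervention on knowledge about diabetes and related health behavior changes", and shortly afterwards that "the outcome variable (Y) was test scores". The schedule places the health-behaviors section in the pretest and again in the posttest at about 30 days. The immediate posttest covers health literacy only. The protocol calls no outcome primary.

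**SAP Section 3** opens with "This section will present the outcomes investigated to answer the study aims and objectives". It then lists two primary outcomes. The first is change in a knowledge composite; the second is "Changes in self-reported behaviors related to diet, exercise, and smoking habits as measured by a composite score".

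**SAP Section 5** gives each outcome its own analysis of variance at 0.05. For behavior: "On factor Analysis of Variance (ANOVA) will be used to compare the differences with an a priori level of 0.05". The opening words are evidently a slip for a one-factor ANOVA. No covariate enters either model, and no rule says how the two results combine.

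**The concern.** Diet and exercise appear as covariates in one document and inside a primary outcome in the other. The protocol also names its outcome variable in the singular, and the only score it describes is the count of correct knowledge answers. Read strictly, that gives one outcome in the protocol and two in the SAP.

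If that reading were right, a significant behavior result would be primary evidence of impact under the SAP but a finding about a covariate under the protocol. The dates add to the unease. The protocol puts recruitment and intervention in October to December 2020, and the SAP is dated December 16, 2021. A reader could ask whether behavior was raised to primary status after the data were in. A second test at 0.05 without a combination rule also raises the usual multiplicity question.

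**Working it through.** **1. The documents side by side.**

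| Question | Protocol (Outcome) | SAP |
|---|---|---|
| Is any outcome labelled primary? | No | Yes, two (Section 3) |
| Is an effect on behavior an aim? | Yes: "we tested the effect of the educational intervention on knowledge about diabetes and related health behavior changes" | Yes: Section 1 states the same pair, knowledge and behavior |
| Is behavior measured so that change can be computed? | Yes: pretest and about 30 days | Yes: the analysis population needs the pretest and the 30-day posttest (Section 4) |
| Is behavior scored? | No scoring described | Yes, as a composite |
| Is covariate adjustment specified? | No; covariates are only listed | No; one-factor ANOVA |

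A conflict over the primary set needs two documents that each define one. Only the SAP does. On aim and on measurement the two documents agree.

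**2. Covariate and outcome together.** The pretest measures behavior before the videos are shown, so baseline behavior can be a covariate. The difference between pretest and 30 days can be an outcome. The two roles do not compete. The protocol never says that its covariates will be adjusted for, so their absence from the SAP's ANOVA contradicts nothing.

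**3. The singular outcome variable.** The protocol uses pretest and posttest as names for whole questionnaires that contain the behavior section. Test scores may therefore cover behavior or knowledge alone. Because scoring is described only for knowledge, the term is ambiguous, but it does not exclude behavior.

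**4. What two tests at 0.05 imply.** The plan states no family-wise error rate, so there is no figure to reproduce. With both null hypotheses true:

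- Independent tests: 1 − (1 − 0.05)² = 0.0975.
- Correlated tests, bivariate normal, two-sided: 0.0907 at correlation 0.5 and 0.0704 at 0.9. The correlations are assumed; the documents give none.
- Two separate claims: 0.05 for each.
- Both required: at most 0.05 for the joint claim.

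Only a rule that either result suffices would produce 7.0% to 9.75%, and the SAP states no such rule.

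**5. Effect on the analysis.** An analyst following SAP Section 5 computes two composite changes, fits two one-factor ANOVAs and reports two p-values, each at 0.05. Rewording the protocol to name two outcomes, or to confine the covariate entry to baseline behavior, leaves all of that as it is.

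**The case for a change.** The strongest case for acting is that the outcome variable is singular, the only scoring rule concerns knowledge, and the protocol's silence on what is primary means that it cannot confirm the SAP's pair. The reading also affects power. With an assumed 21 v 20 split (the diagnosis groups) and a standardized difference of 0.9, one test has 80% power. A rule requiring both outcomes to succeed, with 0.9 on each, has 64% (correlation 0) to 75% (correlation 0.9). A sentence on behavior's role would cost little.

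Part of this stands. The protocol paragraph is inconsistent in its wording. The behavior content also differs: the protocol's examples include healthcare maintenance, while the SAP names smoking. The protocol's list is given as examples, however, and the SAP's definition is the one that governs the score.

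The rest does not carry the point. The power range compares success rules that neither document adopts. It also uses the diagnosis groups, whereas SAP Section 5 compares intervention with control and gives no sizes. An assumed 31 v 10 split alone lowers 80% to 67%. Which groups are compared is a separate question and is not settled here.

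On timing, the SAP's date does not show that results had been seen. The protocol, itself written in the past tense, does not prove that behavior's role was fixed in advance either. It does show that behavior was a tested effect measured twice, so the SAP did not introduce it. A new sentence about its role would not resolve the question of dates.

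**Conclusion.** No change to the plan follows. The inconsistency is real but lies in the protocol's wording: one paragraph lists behavior with the covariates, says an effect on it was tested, and names a single outcome variable. The SAP resolves this by naming two primary outcomes and one test for each, and an analyst can follow it without guessing.

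Two separate tests at 0.05 are acceptable in a study that the SAP calls a pilot, provided the results are read as two claims at 5% each. The 7.0% to 9.75% figure would become relevant only if success on either outcome were presented as success of the study. It rests on assumed correlations of 0.9 down to 0 and on both null hypotheses being true. A correction tied to a rule that the plan does not state would bring no clear gain.

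This conclusion assumes that the ANOVA is one-factor and that the SAP governs the analysis where the protocol is silent.
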